4.0 Inclusion and Exclusion Criteria/ Study Population

Participants: AA adolescents and their primary caregivers or legal guardians (collectively called “families”) recruited from South Carolina communities with Rural-Urban Commuting Area (RUCA) codes 4 – 10. For the Social Support (SS) treatment condition, supporters (family members or friends) will be invited by the family after agreement on the individual by the AAAO and the caregiver. Supporters must be 18 years of age or older to participate.

Community Healthcare Workers (CHWs): All community health workers (CHWs) hired for the intervention will be invited to participate in the usability assessment and focus groups (Aim 2). These participants must have a bachelor’s degree in Psychology, Public Health, or related field and must complete the study training requirements. CHWs who meet the hiring and training requirements for the existing RCT FIT Families (HL155793) will be eligible for hire as CHWs and as study participants. Existing FIT Families CHWs will be our primary recruitment base. New CHWs joining the study will be required to meet the FIT Families study’s requirements for hiring prior to becoming a part of the study.

Inclusion criteria for families:

- 1) Adolescents (ages 12-17) self-identifying as AA
- 2) Adolescent BMI \geq 90th percentile for age and gender
- 3) Primary caregiver either overweight (BMI 25.0 to 29.9) or obese (BMI \geq 30) and willing to participate in treatment
- 4) Adolescent residing primarily with the primary caregiver in a rural community (RUCA Codes 4-10)
- 5) Both caregiver and adolescent must have (separate) Android or Apple (iOS) smartphone with mobile internet connection
- 6) Adolescent and caregiver are English proficient
- 7) Supporters must be 18 years of age or older

Exclusion criteria for youth only:

- 1) Obesity secondary to medication use for another medical condition (e.g., steroids, antipsychotics)
- 2) Obesity secondary to a chronic condition (e.g., Down syndrome, Prader-Willi syndrome, Cushing’s syndrome)

Exclusion criteria that apply to both adolescents and caregivers:

- 1) Pregnancy (e.g., caregivers and youth will be asked each week if they expect if they are pregnant)
- 2) Mental/emotional disorder (e.g., schizophrenia or other psychosis), suicidal, or homicidal
- 3) Serious cognitive impairment (e.g., inability to complete questionnaires)
- 4) Medical condition where weight loss is contraindicated
- 5) Receiving or planned to receive other obesity treatments (e.g., pharmacologic treatment, bariatric surgery) within the next 6 months

Individuals with mild mental retardation may be included if capable of reading and understanding study measures; however, youth/caregivers with more serious cognitive impairments are excluded.

Inclusion criteria for CHWs:

- 1) Bachelor's degree in Psychology, Public Health, or related field
- 2) Completion of the study training requirements
- 3) Completed the three-month study (for focus group participants only).

Exclusion criteria for CHWs:

There are no exclusion criteria.

5.0 Number of Subjects

The study will include 16 African American adolescents with obesity and their overweight or obese primary caregiver for a total of 32 participants. There will also be 8 social support persons for the 8 families that are assigned to the SS condition.

The study will also include 2 community health workers.

6.0 Setting

Study participants will be recruited through posting flyers in public places located within rural areas in South Carolina that meet the RUCA codes 4-10. Potential study participants will contact the study PI with any questions about the study.

The entire study will be conducted on the virtual platform, including the focus groups in Aim 2. CHW training will be conducted at the offices of the Division of Global and Community Health at the Medical University of South Carolina in Charleston, SC.

7.0 Recruitment Methods**Caregivers and Adolescents:**

The research recruitment team will consist of one research assistant and the project manager ([name]). Caregivers and adolescents will be recruited through flyers advertising the study in community spaces (i.e., churches, schools, workout centers, community centers) in South Carolina communities that meet the RUCA 4 – 10 inclusion criteria. The recruitment flyer will contain a QR code which can be scanned by the potential participant on their mobile phone. The QR code will link the potential participant to a web-based pre-screen tool which contains a self-report of height and weight, gender, and age for the adolescent and for the caregiver. Additionally, there will be a statement that asks the following: "Are you the parent, legal guardian, or primary caregiver of an African American adolescent (age 12 – 17) that you think is overweight and/or obese?" Once this information is entered, a calculation of BMI is automatically conducted and the value is compared to the ≥ 90 percentile benchmark for the given data. If the adolescent meets the ≥ 90 percentile for their respective gender and age and the caregiver's BMI is ≥ 25.0 , a message will be shown stating "You may be eligible for this study! Would you like to be contacted to find out more about enrolling in this study?" If the participant agrees then they will be prompted to enter their year of birth (to confirm that the individual indicating a desire to be contacted is the caregiver and not the adolescent), a contact phone number, a best time for contact, and caregiver name. The adolescent will not be permitted to enter contact information or request to be contacted

without the caregiver. If the potential participant responds that they are not the caregiver of a qualifying child or the BMI percentile is outside the included range for the study, then the potential participant will receive a message: "You are not eligible for this study but thank you for your interest."

The respondents to the flyer and pre-screen tool that meet the study criteria and desire to be contacted will then be contacted by phone by the research assistant using the preferred time given. The research assistant will then confirm the participants' height, weight, age, and gender entries for the BMI calculation. Additionally, the research assistant will ask the participant for their home address which will be entered into the "Am I Rural" online screening tool to determine the RUCA code at the participant's zip code of residence. After confirming the address, BMI for adolescent, and overweight/obese status of the caregiver, the research assistant will confirm the availability of compatible mobile devices and a negative pregnancy status. If all criteria are met, the research assistant will ask the participant if they are interested in enrolling in the study, at which point they will be transitioned to the consenting process (below).

Community Health Workers:

All Community Health Workers hired to deliver the study intervention will be asked to participate in the study by a non-supervisor research team member.

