Self-Monitoring (SM) Assessments: Throughout the study, participants will complete assessments via the conversational interface of the mobile app. At the beginning of the intervention (T0), participants will complete a baseline assessment focused on their current engagement in- and perception of-healthy behaviors (eating habits and physical activity level). This assessment will be adapted from the Patient Health Engagement (PHE) Scale⁴⁸. The same questions regarding patient engagement will also be asked at each assessment time point (T1 – T3). The DWN will prompt the participants daily to use the SM feature of the mobile app to complete an assessment that will determine their daily implementation of the physical activity tasks and cognitive behavioral skills learned. For example, participants will be asked to complete a food log that documents the amounts of fruits and vegetables, junk food, water, protein, and whole grains consumed each day. These food types and their suggested quantities are detailed in the nutrition education learning modules. The DWN will also conduct weekly assessments, initially only asking participants to weigh themselves and record their body fat. As the intervention progresses, in collaboration with the CHW they will also be asked to set their weekly treatment goals and reflect on their goals from the past week (barriers that prevent them from reaching their goals and if they need to modify their goals). As a part of SM component, the caregiver and CHW are notified when the AAAO submits or misses submitting an assessment. Once an assessment is submitted, the caregiver reviews the adolescent's progress. If the AAAO does not submit the required assessment or if the caregiver does not review one, the CHW is alerted, and they have the option to reach out directly to the participants through the messaging feature.

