9.0 Study Design / Methods

Study participation will last 3 months. Families who consent to participate will be instructed to download the DWN app and complete a demographics survey. The research assistant will schedule the first session with the CHW and mail the weight scale, yoga mat, resistance bands, and Fitbit Inspire 3s to the family. Families will be randomly assigned to one of two intervention groups: the DWN-FIT or the DWN-FIT_Social Support (SS) group. CHWs will meet with families once a week for 3 months via video chat interface on the DWN-FIT app. The sessions will last approximately 45-minutes to 1 hour and will include: 1) review of SM goals; 2) review of PA steps and calories burned; 3) goal setting based on assessments and learning modules; and 4) review of CBST learning modules using evidence-based steps for skill acquisition (discussion of rationale, modeling of skill, caregiver and AAAO behavioral rehearsal of skill, feedback), and caregiver and AAAO develop implementation plans for between session skills practice.

We will also conduct a focus group with the participants after W12 of the study. These 17 focus groups (16 with participants and support person and 1 with all CHWs) will be guided by the responses to the needs analysis and usability evaluation; however, the questions will be open-ended to encourage discussions to obtain a fuller understanding of their personal experiences using the DWN. We will subsequently transcribe the audio recordings and group the data based on the discussion questions. Then, we will use either an inductive thematic analysis or a bottom-up technique to identify themes or recurring patterns in the responses. Caregivers, AAAOs, Supporters, and CHWs will be compensated \$195.55 for participating in a focus group.

Aim 1: Feasibility Testing. Evaluate the DWN-FIT intervention (delivered by 2 CHWs) with 16 families (AAAO and caregiver, overweight or obese) undergoing treatment for adolescent obesity to determine the degree to which the components of the digital intervention are correlated with adolescent-caregiver engagement in healthy behaviors and adherence to the prescribed treatment. Additionally, we will determine the degree to which SS, as an additional element of DWN-FIT, enhances engagement and retention of families within treatment.

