Methods: This aim follows two conditions (DWN-FIT vs DWN-FIT_Social Support [SS]) x 4 time (T0: baseline, T1: 1-month follow-up, T2: 2-month follow-up, and T3: 3-month end of treatment), with random assignment of 16 families (caregivers/AAAO) to one of the two treatment conditions. The proposed 3-month treatment period is too short to assess the feasibility of this digital treatment with respect to weight loss measurements (secondary outcomes), so instead we will assess feasibility of this approach based on the development of healthy behaviors (primary outcomes) that have been shown to lead to sustainable weight loss over time. Primary outcomes will be measured after each session (weekly) through the data recorded by the DWN app. These primary measures consist of the following measurements via the DWN app: step count, PA and PA video views, frequency and consistency of nutrition SM, messaging read and response rates, frequency and consistency of CBST education participation, telehealth session attendance, and CM rewards. In both treatment conditions, we will determine correlation between these measures and our measures of engagement and adherence. We will also determine the effect of semi-automated SS on each of the measures by comparing outcomes from each treatment group (DWN-FIT vs DWN-FIT_SS). Caregiver and AAAO percent

overweight and body-mass index (BMI) will serve as secondary outcome measures and will be collected each week via a provided digital scale. These secondary outcomes will be used to build preliminary data for a future full time-course (6-month or greater) randomized clinical trial (RCT).

Measures: We will measure **engagement** through the delivery of the 9-item Patient Health Engagement (PHE)⁴⁸ survey. The PHE is used to determine the degree to which patients are engaged in their own health and describes the patient's ability to manage their own health. PHE has been validated in other work, but a sample size large enough to meet this threshold is outside the scope of this study. The PHE outcomes gathered here will be used as preliminary data for future studies. The PHE survey will be taken via the DWN app at each time point, T0-T3. We will measure **adherence** through comparing the prescribed tasks against the task completed, raw counts (video views, SM entries, PA participation), by each set of participants. We will explore how SS is correlated with adherence to the prescribed treatment.

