Aim 2: Patient Centered Evaluation. Conduct a needs analysis before the intervention, a usability evaluation during the intervention and focus groups with participants after the intervention to determine if DWN met their needs for accessing (participants), delivering (CHWs), and providing support during the treatment.

Needs Analysis: We will develop a pre-survey (at T0 guided by [name]) consisting of a set of qualitative questions that determine the participants' goals and needs related to accessing, delivering, and providing support during the treatment. After completion of the intervention (T3), we will conduct a post-survey to determine if DWN-FIT met their needs and goals. Using responses from these two surveys, we will perform an inductive thematic analysis or a bottom-up technique to identify themes or recurring patterns in participants' responses.

Usability Evaluation: We will deliver a usability assessment via the System Usability Scale (SUS)⁴⁹ assessment that will be delivered to the participants at the midpoint of the intervention; it will focus on the efficiency and effectiveness of accessing, delivering, and providing support during the treatment including such topics such as readability, technology literacy, and interface design.

Construct	Measure / Items	Information / Data Source	When Completed*													
			0	1	2	3	4	5	6	7	8	9	10	11	12	13-16
Eligibility/Screening Criteria																
%Overweight	• Body Mass Index (BMI; height and weight measurements)	Youth & CGs	✓													
Primary Outcome Measure																
% Body Fat	• Bioelectrical impedance analysis (BIA)	Youth & CGs		✓	✓	✓	✓	✓	✓	✓	✓	✓	✓	✓	✓	✓
Secondary Outcome Measure																
Physical Activity (PA)	• Fitbit Inspire 2 accelerometer	Youth & CGs		✓	✓	✓	✓	✓	✓	✓	✓	✓	✓	✓	✓	✓
	• Fitbit data	Youth & CG Fitbit		✓	✓	✓	✓	✓	✓	✓	✓	✓	✓	✓	✓	✓
Self-Monitoring of Dietary Intake	• Food/Beverage Log	Youth & CGs		✓	✓	✓	✓	✓	✓	✓	✓	✓	✓	✓	✓	✓
Clinical Note	• Meeting participants	CHW		✓	✓	✓	✓	✓	✓	✓	✓	✓	✓	✓	✓	✓
	• Meeting Duration	CHW		✓	✓	✓	✓	✓	✓	✓	✓	✓	✓	✓	✓	✓
	• Learning module content review	CHW		✓	✓	✓	✓	✓	✓	✓	✓	✓	✓	✓	✓	✓
	• % body fat	CHW		✓	✓	✓	✓	✓	✓	✓	✓	✓	✓	✓	✓	✓
	• Pregnancy screening question	CHW		✓	✓	✓	✓	✓	✓	✓	✓	✓	✓	✓	✓	✓
	• General notes	CHW		✓	✓	✓	✓	✓	✓	✓	✓	✓	✓	✓	✓	✓
Daily Activity Summary	• Food Log Completion	Youth & CGs	✓	✓	✓	✓	✓	✓	✓	✓	✓	✓	✓	✓	✓	✓
	• Number of Steps Taken	Youth & CGs	✓	✓	✓	✓	✓	✓	✓	✓	✓	✓	✓	✓	✓	✓

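### BMI and percent overweight are to come weekly from a scale, but height is obtained once, by self-report, so adolescents' within-person 3-month BMI change is biased upward if they grow

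*Protocol*

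**What the plan says.** **Outcome.** Protocol section 9.0 (Aim 1, Methods) states that caregiver and adolescent percent "overweight and body-mass index (BMI) will serve as secondary outcome measures and will be collected each week via a provided digital scale". These outcomes are meant to supply preliminary data for a longer randomised trial.

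**Source of height.** Section 7.0 describes a "web-based pre-screen tool which contains a self-report of height and weight, gender, and age" for the adolescent and the caregiver. The research assistant then confirms by phone the "height, weight, age, and gender entries for the BMI calculation". No other way of obtaining height is described.

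**Schedule.** The table in section 9.0 lists "Body Mass Index (BMI; height and weight measurements") under eligibility and screening, with one mark, at week 0. No later row lists height.

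**Weekly collection.** Section 3.0 (Self-Monitoring) describes weekly assessments "initially only asking participants to weigh themselves and record their body fat". Goal setting is added later, but height is not.

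**Setting and equipment.** Section 6.0 says: "The entire study will be conducted on the virtual platform". After consent, the research assistant is to "mail the weight scale, yoga mat, resistance bands, and Fitbit Inspire 3s to the family" (section 9.0). That list contains no device for measuring height.

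**Population.** Section 4.0 admits "Adolescents (ages 12-17) self-identifying as AA".

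**The concern.** BMI needs a weight and a height. The Methods text promises a weekly BMI from an instrument described only as giving weight (and, in section 3.0, body fat), while the schedule shows BMI once, for screening. Followed as written, every weekly BMI has to reuse the height given at pre-screening.

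For an adult that does little harm to a change score. For a 12 to 17 year old who is still growing, the week-12 weight is divided by a height that is too small, so the final BMI is too high and a fall in BMI is understated. At stake is the within-person change in adolescents that this pilot would pass on to the next trial. The loss is one of data collection: a height that was never taken cannot be recovered at analysis.

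**Working it through.** The protocol gives no figure for BMI change, so there is none to reproduce. The check is direct arithmetic.

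**Inputs from the protocol.** Age 12 to 17 (section 4.0); 3 months of participation (section 9.0); 16 adolescents and 16 caregivers, with 8 of the 16 families in the social support arm (section 5.0); one pound as a weight-loss yardstick in the bonus rule (section 3.0).

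**Assumptions, not in the protocol.** A reference adolescent of 1.65 m and 85 kg; growth of 0 to 2 cm in 3 months; a 2 kg under-report of weight at pre-screening.

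**1. Frozen height.** With baseline height h, growth g and final weight W, the overstatement of final BMI, and so of the change, is W/h² − W/(h+g)².
- g = 0 cm: 0
- g = 1 cm: 85/1.65² − 85/1.66² = 31.22 − 30.85 = 0.38 (from unrounded values)
- g = 2 cm: 85/1.65² − 85/1.67² = 31.22 − 30.48 = 0.74

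At 1.60 m and 90 kg the same formula gives 0, 0.44 and 0.86.

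**2. Scale of the error.** One pound (0.454 kg) is 0.454/1.65² = 0.167 units, so 1 cm of missed growth hides about 0.38/0.167 = 2.3 lb of loss. Losing one pound a week for 12 weeks (5.44 kg) is 5.44/1.65² = 2.00 units.

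**3. Constant error in the reported height.** If the same wrong height enters every BMI, the change is only rescaled, by (h/(h+e))². For e from −2 to +3 cm at 1.60 m that is +2.6% to −3.7%. A true change of −1.95 units (5 kg lost) would appear as −2.00 to −1.88. This is minor, and it is the only height error that applies to caregivers.

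**4. Baseline weight, conditional.** If the self-reported weight served as T0 and scale weights followed, an under-report of u kg adds u/h² of false gain. For 2 kg this is 2/1.65² = 0.73, or 2/1.67² = 0.72 if height was over-reported by 2 cm. Over-reporting weight would act in the opposite direction.

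**5. Between arms.** Growth has the same expectation in both randomised arms, so its error cancels in expectation. Chance imbalance remains. At 1.60 m and 90 kg, each centimetre is worth 2 × 90/1.60³/100 = 0.44 units. With an SD of growth of 0.4 to 0.7 cm (assumed) and 8 per arm, the SE of the arm difference from this source is 0.44 × SD × √(2/8) = 0.09 to 0.15 units.

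**The case against.** **Mixed weight sources.** A reader might infer that the BMI change must set a self-reported week-0 weight against later scale weights. The protocol does not say so. Section 7.0 uses self-report for eligibility, the schedule files the week-0 BMI under screening and calls its components measurements, and section 9.0 attributes the outcome to the scale throughout. The first scale weight may well be the intended baseline. This objection stands: the baseline is undefined, and step 4 applies only under one reading.

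**A larger figure.** A reader might also add a 2 kg under-report of weight to a 2 cm over-report of height and obtain 85/1.65² − 83/1.67² = 31.22 − 29.76 = 1.46 units. That is an error in the week-0 BMI level. With the same height carried forward, the error in the change is 30.48 − 29.76 = 0.72, and only if self-reported weight is the baseline.

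**Treatment comparison.** It would be wrong to infer that the comparison of DWN-FIT with DWN-FIT_SS is biased. Growth cancels in expectation, and the pre-screen report precedes randomisation, so differential misreporting is not expected.

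**Importance.** The outcomes are secondary, section 9.0 itself considers 3 months too short for weight loss, and some adolescents will have stopped growing. All of this stands and keeps the point small.

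**Left to the analysis plan.** Which weight is baseline and how percent overweight is computed could be specified in an analysis plan. Whether height is measured again could not be repaired there.

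**Noise in the remedy.** Two home measurements have error of their own. With an SD of 1 cm each (assumed), their difference has an SD of √2 = 1.4 cm. At 1.65 m and 85 kg, where 1 cm is worth about 0.38 units, that is about 0.5 BMI units per adolescent, similar in size to the growth error. But it is random: over 16 adolescents the mean has an SE of about 0.5/√16 = 0.13 units, whereas the growth error does not average out.

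**Conclusion.** The point holds for adolescents' within-person BMI change. The Methods text and the schedule in section 9.0 disagree on whether BMI is a weekly outcome or a single screening item, and following the protocol leaves one self-reported height for the whole study. The resulting upward bias is about 0 to 0.74 units at 1.65 m and 85 kg. It rests on assumed growth of 0 to 2 cm and is zero where growth has stopped. A further 0.7 units or so arises only if the self-reported weight is the baseline and is 2 kg too low.

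Percent overweight shares the height problem for adolescents, but its error cannot be sized because the protocol gives no formula. Caregivers' change is not affected by growth, and the arm comparison is not biased in expectation. The point is a minor improvement, worth making because the missing heights cannot be supplied later.

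**What to change.** Reconcile section 7.0 with the Methods text and the schedule in section 9.0:

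1. Use self-reported height and weight for pre-screening only.
2. Name the first weight from the provided scale as the baseline for change.
3. Measure height by a standard method on video at T0 for adolescent and caregiver, and again at T3 for the adolescent.
4. Compute BMI and percent overweight from those values, and state which height is used for the adolescent in the weeks between.
5. Mark the weekly weights and the T0 and T3 heights in the schedule.

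The cost is a tape measure in the mailed kit, a few minutes at two existing video sessions, and some random measurement error in height.
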